13.5.6.2 Efficacy Endpoints Regarding Response

For endpoints regarding response (30%, 50%, 75% or 100%) or sustained response (75%), the number and percentage of responders using weekly number of attacks for Week 1, Week 2, Week 3, Week 4, Week 5,, Week 48 and the number and percentage of responders using monthly number of attacks for Month 1, Month 2,, Month 12 will be presented without imputations other than described in section [13.5.1.1.1](#). Additionally, sensitivity analyses will be made using LOCF and worst case imputations, for further details see section [13.5.9.3](#). For all of these analyses DPS3 will be used when determining whether a participant is a responder or not.

Furthermore, the number and percentage of responders will be found for the following periods of time (for details see section [23.2.1.7](#)):

- Months 1-3, Months 4-6, Months 7-9, Months 10-12
- Months 1-6, Months 7-12

- Months 1-12

13.5.6.3 Other Efficacy Endpoints

Endpoints that are not covered by sections [13.5.6.1](#) and [13.5.6.2](#) will only be summarized descriptively as described in chapter [7](#).

13.5.6.4 Subgroup Analyses

The subgroups to be investigated are participants who are treatment resistant and participants who are not (see section [23.2.5](#) for a definition of treatment resistant). The endpoint to be considered for these subgroup analyses is Change from Baseline in the number of monthly attacks (Months 1,2, ..., 12).

13.5.7 Rationale for Selected Analysis Method for the Secondary and Exploratory Endpoints

The MMRM model is chosen as it is a very flexible and robust analysis, and with the selected explanatory variables it will allow the endpoint to vary freely by visit, account for the baseline level and for country differences, and it includes the most flexible structure for within participant variation. This will allow the use of all participants also those who withdraw or have missing data.

13.5.8 eDiary Reported Use of Medication

In the headache eDiary, participants are asked each day or each week (depending on whether a participant is in a period with daily or weekly registrations) to fill out whether they used any of the following medications during that day/week: oxygen, triptans, or other. The number and percentage of participants taking each of the medication types will be presented for each 4-week interval in the trial including baseline values.

13.5.9 Sensitivity Analyses of Secondary and Exploratory Endpoints

13.5.9.1 Sensitivity Analyses to assess the impact of the use of transitional medication

To assess the impact of the use of transitional treatments, the MMRMs described in sections [13.5.1](#) and [13.5.3](#) will be used to analyse data where all data are included also immediately after receiving a transitional treatment corresponding to a treatment strategy. It will only be done for the endpoints described in sections [13.5.1](#) and [13.5.3](#) respectively.

13.5.9.2 Sensitivity Analyses to assess the impact of the strategy of handling withdrawal from treatment

To assess the impact of the chosen hypothetical strategy for handling withdrawal from treatment the MMRM described in section [13.5.3](#) will be used to analyse data where all data

are included corresponding to a treatment strategy. It will only be done for the endpoint described in section 13.5.3.

13.5.9.3 Sensitivity Analyses to assess the impact of missing data regarding response

To assess the impact of only imputing data by prorating for response endpoints as described in section 13.5.6.2, LOCF and worst case imputations will be carried out for the endpoints regarding 75% response.

14 Safety

14.1 Adverse Events

14.1.1 General Methodology for Adverse Events

Unless otherwise specified, tables, graphs, and listings will be based on the APTS.

Tables by preferred term and tables by system organ class (SOC) and preferred term will be sorted in descending order based on the percentages of participants with these adverse events.

Unless otherwise specified, the summaries of adverse events will include the number and percentage of participants with an adverse event, and the total number of events. In tables displaying SOC or preferred terms, participants are counted only once within each SOC or preferred term.

Listings of adverse events will be sorted by site, treatment group, participant screening number, and adverse event start date, and include preferred term, investigator term, adverse event start date, the date of first IMP infusion, the date and time of the latest IMP infusion prior to the adverse event, the time since latest IMP infusion, duration of the adverse event, action taken, causality, intensity, seriousness, and outcome. Furthermore, sex, age, race and baseline weight will be presented if available. For adverse events that change in intensity, each intensity will be included. In listings of adverse events, start or stop dates will be displayed as collected also in case of partially or completely missing dates.

14.1.2 Coding of Adverse Events

Adverse events will be coded using MedDRA, Version 25.0 or later.

14.1.3 Classification of Adverse Events

Adverse events will be classified according to the time of onset of the adverse event:

- *pre-treatment adverse event* – an adverse event that starts on or after the date the participant signed the *Informed Consent Form(s)* and prior to the date and time of first dose of eptinezumab

- *treatment-emergent adverse event* (TEAE) – an adverse event that starts during or after administration of the first dose of IMP, or a pre-treatment adverse event that increases in severity or becomes serious during or after administration of the first dose of IMP

For handling of adverse events with incomplete start dates to facilitate this classification, see section [23.4.4](#). Note that adverse events with incomplete start dates will be classified as not being treatment-emergent if the causality to IMP is “Not Related - Prior to IMP”.

An adverse event is considered causally related to the use of eptinezumab when the causality assessment by the investigator is *probable* or *possible*. If the causality assessment is missing, the adverse event is considered causally related.

14.1.4 Presentation of Adverse Events

All adverse events will be listed for the APES, including a flag for TEAEs.

The numbers, and percentages of participants with TEAEs, TEAEs leading to infusion interruption, serious adverse events (SAEs), or adverse events leading to withdrawal, and of participants who died will be presented based on the APTS.

14.1.5 Presentation of Treatment-emergent Adverse Events

The following summaries will be provided:

- TEAEs by SOC and preferred term
- TEAEs by preferred term
- TEAEs by sex and preferred term
- TEAEs with an incidence $\geq 2\%$ by preferred term
- causally related TEAEs by SOC and preferred term
- TEAEs by intensity (*mild/moderate/severe*), SOC, and preferred term
- causally related TEAEs by intensity, SOC, and preferred term
- TEAEs occurring on the day of dosing after infusion start by SOC and preferred term (this includes the days of the first, second, third and fourth infusion)
- TEAEs by infusion Periods by SOC and preferred term (this includes time between the start of the first and second infusions, second and third infusions, third and fourth infusions, and within 12 weeks after the start of the fourth infusion)

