16.9.1 Analysis of Adverse Events

Adverse events will be classified according to the time of onset of the adverse event:

- *pre-treatment adverse event* – an adverse event that starts on or after the date the patient signed the *Informed Consent Form(s)* and prior to the date of first dose of eptinezumab
- *treatment-emergent adverse event* (TEAE) – an adverse event that starts or increases in intensity during or after administration of the first dose of eptinezumab

Adverse events, sorted by system organ class (SOC) and preferred term, will be summarised for the full study and by 3-month periods.

Allocation of TEAEs to Study Periods

TEAEs may be allocated to study periods (these will be defined in the *Statistical Analysis Plan*).

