
Objectives	Endpoints
Exploratory Objective 
To explore the target engagement of eptinezumab to calcitonin gene-related peptide (CGRP)	
Exploratory endpointChange from Baseline in CGRP (CGRP-eptinezumab complex, free CGRP) at Weeks 12, 24, 36, and 48

6 Analysis Sets

The following analysis sets will be used to analyse and present the data:

- all-participants-enrolled set* (APES) – all enrolled participants
- all-participants-treated set* (APTS) - all participants in the APES who received infusion with eptinezumab
- full-analysis set* (FAS) - all participants in the APTS who have a valid assessment of the baseline number of weekly attacks and a post-baseline assessment of number of weekly attacks.

The participants and data will be classified into the analysis sets during a *Classification Meeting* according to the definitions above after the trial database has been released, but prior to the headline results meeting.

Safety analyses (including tolerability and exposure), disposition, demographics and baseline characteristics will be based on APTS.

Efficacy analyses will be based on FAS.

Three Data Point Sets (DPS) will be used for presenting the results using eDiary data:

- DPS1: All data points obtained at or after enrolment
- DPS2: All data points obtained at or after enrolment except for those following the 7-day rule after the use of transitional treatment (for details see section 23.2.4)
- DPS3: All data points obtained at or after enrolment except for those following the 7-day rule after the use of transitional treatment (see section 23.2.4) and those following the 12-week rule after withdrawal from treatment (see section 23.2.1.5)

DPS1 will be used for the descriptive statistics described in chapter 7 as well as the sensitivity analyses described in sections 13.5.9.1 and 13.5.9.2, DPS2 will be used for the short-term efficacy estimand described in section 13.5.1, and DPS3 will be used for the long-term efficacy estimand (section 13.5.3), the sensitivity analysis described in section 13.5.9.3, and analyses based on eDiary data. For more details see chapter 13.

For efficacy data not derived from the eDiary all analyses will be based on all data points obtained at or after enrolment.

7 Descriptive Statistics

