14.2 General Methodology for Other Safety Data

Unless otherwise specified, tables, graphs, and listings will be based on the APTS.

The denominators for the summaries of a given variable will be based on the number of participants with non-missing values at a given visit or during the assessment period.

Descriptive statistics for the safety variables, both absolute values and changes from Baseline, will be presented by visit.

The number and percentage of participants with at least one PCS value at any post-baseline assessment time point will be summarized by variable. All available assessments will be included in the evaluation of PCS values.

For participants with post-baseline PCS values, listings will be provided including all the values for those participants for the variable, with flagging of PCS values and out-of-reference-range values.

All the adverse events in participants with post-baseline PCS values will be listed by participant screening number; the listing will include the PCS value, the assessment date, the change from Baseline in PCS value, the preferred term for the adverse event, and start date and stop date of the adverse event. The PCS values and adverse events will be listed in chronological order according to assessment date and the start date of the adverse event.

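### The by-infusion-period table of treatment-emergent adverse events has no at-risk denominator, no end to a period when the next infusion is not given, and no period after Week 48

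*SAP*

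**What the plan says.** SAP 14.1.5 lists among its summaries "TEAEs by infusion Periods by SOC and preferred term (this includes time between the start of the first and second infusions". It continues with the second-to-third and third-to-fourth intervals and closes with the time "within 12 weeks after the start of the fourth infusion". It does not say when one of the first three periods ends if the next infusion is not given.

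The base for the table comes from the general rule in SAP 14.1.1: "Unless otherwise specified, tables, graphs, and listings will be based on the APTS". The same section says that "summaries of adverse events will include the number and percentage of participants with an adverse event", together with the number of events. SAP chapter 6 defines the APTS as "all participants in the APES who received infusion with eptinezumab", so it includes people who stop before infusion two, three or four. Laboratory, vital sign and ECG data have a different rule in SAP 14.2, where denominators are "based on the number of participants with non-missing values at a given visit or during the assessment period". That rule sits under other safety data and does not extend to adverse events.

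On timing:
- Protocol 10.1.1 collects adverse events until the Safety Follow-up (SFU) Visit.
- SAP chapter 2 places that visit at Week 56, 20 weeks after the last infusion.
- SAP 14.1.3 sets no upper time limit on a treatment-emergent adverse event (TEAE).
- Participants withdrawn from treatment may stay for all remaining visits. Otherwise they have an SFU Visit 20 weeks after their last infusion (SAP chapter 2).

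Protocol 16.9.1 says that adverse events "will be summarised for the full study and by 3-month periods" and leaves the definition of periods for TEAEs to the SAP.

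**The concern.** Long-term safety is the primary objective, and there is no control arm. The by-period table is where a reader would look to see whether adverse event incidence changes over successive dosing intervals. Three features make it hard to read.

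1. If every percentage is taken over the APTS, the later periods count people who could not contribute an event because they never started that infusion. An unchanged risk then appears to fall, which could be taken for improving tolerability.
2. A participant whose last infusion is number one, two or three has no next infusion to close the period. One programmer may leave that time out, and another may leave the period open to last contact. The events affected include those that caused the stop. For example, Protocol 6.2 withdraws a participant from treatment after an anaphylactic reaction, so a reaction at infusion one has no second infusion to bound its period.
3. Events between Week 48 and the SFU Visit belong to no period, although that visit exists partly to capture them (Protocol 8.8).

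**Working it through.** **Inputs.** 125 treated, 100 to complete, 20% withdrawal (SAP chapter 20). Infusions at Weeks 0, 12, 24 and 36, and SFU at Week 56 (SAP chapter 2). The documents do not give the timing of withdrawals, so it is assumed and varied. The 10% incidence per period is an illustration.

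**The plan's own figure.** 100 / (1 − 0.20) = 125. This reproduces.

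**Denominator effect.** If the incidence among those who start infusion k is p, and people who never start it contribute no events to period k, the table shows p × n_k / 125, where n_k is the number starting infusion k.

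- Constant hazard: n = 125 × 0.8^(w/48), with w the week of the infusion.
- Linear withdrawal: n = 125 × (1 − 0.20 × w/48).

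| Infusion | n, constant hazard | n, linear | 10% shown as, constant hazard | 10% shown as, linear |
|---|---|---|---|---|
| 1 (Week 0) | 125 | 125 | 10.0% | 10.0% |
| 2 (Week 12) | 118.2 | 118.75 | 9.5% | 9.5% |
| 3 (Week 24) | 111.8 | 112.5 | 8.9% | 9.0% |
| 4 (Week 36) | 105.7 | 106.25 | 8.5% | 8.5% |

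Relative understatement in period four: 1 − 105.7/125 = 15.4% (constant hazard) and 1 − 106.25/125 = 15.0% (linear). The bounds are:
- All 25 leave before infusion two: 1 − 100/125 = 20%.
- All 25 leave after infusion four: 1 − 125/125 = 0%.

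The 12-week withdrawal rates that SAP chapter 20 cites from two other trials (under 4%, and about 7%), carried forward per 12 weeks, give 125 × 0.96³ = 110.6 and 125 × 0.93³ = 100.5. The understatement is then 11.5% and 19.6%, inside the same range.

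**Missing closing rule.** For a last infusion numbered one, two or three, follow-up after it is 20 weeks by the SFU route. For someone who stays in the trial it is up to 56 − 0 = 56, 56 − 12 = 44 or 56 − 24 = 32 weeks. If a period needs both infusions, all of that time is unallocated. If the period is left open, a nominal 12-week period becomes 20 to 56 weeks long.

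**Interaction of the two.** Suppose periods one to three need both infusions, and early stoppers have the same 10% risk. Period one then draws events only from those who reach infusion two and shows 10% × 118.2/125 = 9.5%. Period four still shows 8.5%. The apparent fall from period one to period four becomes 1 − 105.7/118.2 = 10.6% instead of 15.4%, but every period is now too low.

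**Weeks 48 to 56.** For a completer, 8/56 = 14.3% of post-baseline follow-up, and 8/20 = 40% of follow-up after infusion four, has no period.

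**The case against.** **An analysis set is not a denominator.** SAP 14.2 names the APTS and then sets denominators in a separate sentence, and the by-sex TEAE table would naturally be read with one denominator per sex. A reader might infer that the SAP prescribes 125 as the denominator in every period. It does not: that figure follows from the 14.1.1 default because 14.1.5 names nothing else. The dilution is what the text yields if followed as written, and one sentence would remove it.

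**Nothing is lost to the study.** A reader might infer that early stoppers' events or Week 48 to 56 events go unreported. They do not. SAP 3.2 reports treatment and follow-up as one period unless otherwise specified, 14.1.4 lists all adverse events, and 14.1.8 tabulates those leading to withdrawal. The gap is confined to the by-period table.

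**It is not the only view of repeated dosing.** SAP 14.1.5 also summarises infusion-day TEAEs and names all four infusions, and the listings give time since the latest infusion (14.1.1). What stands is that no other summary covers whole dosing intervals.

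**The effect is small.** The illustrated artefact is 1.5 percentage points, against a standard error of √(0.10 × 0.90 / 106) = 2.9 points, and no testing is planned. That is fair for any single term. But this is a systematic error that pulls every row the same way, so sampling error does not average it out.

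**A reader could recompute it.** SAP chapter 11 reports infusions received at each infusion visit, so the percentages can be rebuilt from the counts. That repairs the denominator but not the allocation of events to periods.

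**Conclusion.** The point holds as a defect in the specification of one descriptive safety table. As written, SAP 14.1.5 gives later-period percentages on a base that includes people who never started the infusion. It also leaves TEAEs after an early last infusion without a defined period, and Week 48 to 56 TEAEs in none.

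The denominator effect in period four is about 15% relative under constant-hazard or linear withdrawal, with a range of 0 to 20%. This assumes that the planned 20% is the share who stop infusions. The plan states it as loss before completion, and someone who stops infusions but stays in the study counts as completing (SAP 3.3), so the true share could differ.

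The direction is also not certain for the table as a whole. Leaving out early stoppers' events lowers the early periods too, and leaving a period open inflates the last one that a participant started. The supportable statement is that a constant risk could look like a falling one. The documents do not show that it will, nor that it would by a fixed 15%.

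**What to change.** Amend SAP 14.1.5 as follows.

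- **Denominator:** for each period, the participants who started the infusion that opens it.
- **End of period:** the start of the next infusion whenever that is given. Only if no further infusion is given, 12 weeks after the participant's last infusion. Cutting at 12 weeks regardless would open a new gap, because infusion visits have a ±3-day window (Protocol Panel 2). With infusion two on Day 87, events from Day 84 until that infusion would have no period.
- **Follow-up column:** all later TEAEs, up to last contact or the SFU Visit, so that every TEAE falls in exactly one period.
- **Participant-time or an exposure-adjusted rate beside the follow-up column:** its length varies. It is 20 − 12 = 8 weeks for completers and for those on the SFU route, and up to 56 − 12 = 44 weeks for someone who stops after infusion one and stays in the trial.

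The cost is SAP wording and table programming. No new data are needed, and the overall TEAE tables and listings do not change.

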14.1.6 Presentation of Deaths

All the adverse events in participants who died will be listed for the APES.

14.1.7 Presentation of Serious Adverse Events

All the SAEs will be listed for the APES.

Treatment-emergent SAEs will be summarized based on APTS by:

- SOC and preferred term
- preferred term

14.1.8 Presentation of Adverse Events Leading to Withdrawal

All the AEs leading to withdrawal will be listed for the APES.

TEAEs leading to withdrawal will be summarized by:

- SOC and preferred term
- preferred term

14.1.9 Presentation of Adverse Events leading to Trial Drug Infusion Interruption or Termination

All AEs leading to trial drug infusion interruption or termination will be listed for the APES.

TEAEs leading to trial drug infusion interruption or termination will be summarized based on APTS by:

- SOC and preferred term

14.1.10 Presentation of Adverse Events of Special Interest

Treatment-emergent adverse events of special interest (AESI) will consist of the preferred terms defined by the SMQs/HLTs/HLGTs listed in [Table 5](#).

The following summaries of treatment-emergent AESIs will be provided:

- AESIs by SOC and preferred term
- AESIs by SOC and preferred term, separately for each individual event category

The summaries will be provided for the APTS.

14.2 General Methodology for Other Safety Data

Unless otherwise specified, tables, graphs, and listings will be based on the APTS.

The denominators for the summaries of a given variable will be based on the number of participants with non-missing values at a given visit or during the assessment period.

Descriptive statistics for the safety variables, both absolute values and changes from Baseline, will be presented by visit.

The number and percentage of participants with at least one PCS value at any post-baseline assessment time point will be summarized by variable. All available assessments will be included in the evaluation of PCS values.

For participants with post-baseline PCS values, listings will be provided including all the values for those participants for the variable, with flagging of PCS values and out-of-reference-range values.

All the adverse events in participants with post-baseline PCS values will be listed by participant screening number; the listing will include the PCS value, the assessment date, the change from Baseline in PCS value, the preferred term for the adverse event, and start date and stop date of the adverse event. The PCS values and adverse events will be listed in chronological order according to assessment date and the start date of the adverse event.

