3.2 Rationale for the Study Design

The current study is planned as fixed-dose, multiple infusions study with an open-label design. The duration of the Treatment Period is chosen to allow generation of long-term exposure safety and tolerability data in patients with cCH, upon multiple infusions with eptinezumab 400 mg. The duration of the Screening Period is chosen to inform on the baseline disease activity in a population of patients with cCH who are managed according to the established standards of care.

The proposed study population are patients with cCH. Episodic cluster headache and cCH share common pathophysiology and overlapping clinical symptoms with the major differences between the two forms of cluster headache residing in the duration of the “active” and “remission” periods and, very important from a clinical point of view, patients with cCH have a very poor response to preventive medications.³⁸ The distinctions in two separate forms is, in some cases, solely virtual as when exacerbations lengthen, remissions shorten or more clusters occur than usual, the sufferers might be switching from episodic to chronic cluster headache.³⁹ Unhealthy lifestyle factors like smoking, alcohol overuse and high body mass index (BMI) are common for patients with episodic cluster headache and cCH and several

lifestyle related diseases like metabolic disease, gastric ulcer, menstrual diseases in women and visual disorders are being more frequently reported in cCH than in episodic cluster headache.⁴⁰ Therefore 1-year exposure to eptinezumab of patients with cCH, is considered an acceptable conservative approach to generate safety and tolerability data to adequately support the data, generated in the ongoing Phase III study in episodic cluster headache sufferers (19386A). In addition, the patients with cCH are the patient population, in need for long-term treatment to alleviate the symptoms of cluster headache.

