16.9.2 Analysis of Other Safety Endpoints

Absolute values and change from baseline for vital signs, weight, ECGs, clinical safety laboratory test values will be summarised by visit. The number of patients exceeding the PCS values will be tabulated. The incidence, kinetics and magnitude of ADA and NAb response(s) will be evaluated.

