4 COVID-19

For this trial, all participants are considered to have been enrolled after the beginning of the COVID-19 outbreak.

The following information is collected with regards to COVID-19:

- Whether a visit was done remotely due to COVID-19 including which assessments were/were not performed
- Whether participants withdrew due to the COVID-19 situation
- Whether participants got diagnosed with COVID-19

Remotely done visits will be tabulated or listed as appropriate. Participants diagnosed or withdrawn due to COVID-19 will be seen from tables/listings of AEs and AEs leading to withdrawal respectively.

5 Endpoints

The endpoints are summarized in [Panel 2](#). There are no key secondary endpoints in this trial.

Panel 2 Endpoints

Objectives	Endpoints
Primary Objective 
 To evaluate the long-term safety and tolerability of eptinezumab in participants with chronic cluster headache (cCH) 	
 Primary endpoints: 
 - adverse events - absolute values and changes from Baseline in clinical safety laboratory test values, vital signs, weight, and electrocardiogram (ECG) parameter values - potentially clinically significant (PCS) clinical safety laboratory test values, vital signs, weight changes, and ECG parameter values - development of specific anti-eptinezumab antibodies (ADAs) including neutralizing antibodies (NABs) - Columbia-Suicide Severity Rating Scale (C-SSRS) score

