Appendix III

PCS Criteria

PCS Criteria

Table 1 PCS Criteria for Clinical Safety Laboratory Tests

Laboratory Test	CDISC Term	Unit	PCS Low	PCS High
Haematology / Coagulation				
B-haemoglobin	HGB	g/L	≤ 95 (women) ≤ 115 (men)	≥ 165 (women) ≥ 185 (men)
B-erythrocytes (red cell count)	RBC	x 10E12/L	≤ 3.5 (women) ≤ 3.8 (men)	≥ 6.0 (women) ≥ 7.0 (men)
B-haematocrit (packed cell volume)	HCT	V/V	≤ 0.32 (women)	≥ 0.50 (women)
			≤ 0.37 (men)	≥ 0.55 (men)
B-MCV (mean cell volume)	MCV	fL	≤ 0.8 x LLN	≥ 1.2 x ULN
B-total leucocyte (white cell count)	WBC	x 10E9/L	≤ 2.8	≥ 16
B-neutrophils/leucocytes	NEUTLE	%	≤ 20	≥ 85
B-eosinophils/leucocytes	EOSLE	%		≥ 10
B-basophils/leucocytes	BASOLE	%		≥ 10
B-lymphocytes/leucocytes	LYMLE	%	≤ 10	≥ 75
B-monocytes/leucocytes	MONOLE	%		≥ 15
B-thrombocytes (platelet count)	PLAT	x 10E9/L	≤ 75	≥ 600
P-INR (prothrombin ratio)	INR	Ratio		≥ 2.0
B-prothrombin time	PT	Sec		≥ 18
Liver				
S-aspartate aminotransferase	AST	I/L		≥ 3 × ULN
S-alanine aminotransferase	ALT	I/L		≥ 3 × ULN
S-bilirubin	BILI	µmol/L		≥ 34
S-bilirubin, direct	BILDIR	µmol/L		≥ 12
S-bilirubin, indirect	BILIND	µmol/L		≥ 22
S-alkaline phosphatase	ALP	I/L		≥ 3 × ULN
S-gamma glutamyl transferase	GGT	I/L		≥ 200
S-alpha-glutathione S-transferase (alpha-GST)	GSTAL	µg/L		≥ 20
Kidney				
S-creatinine	CREAT	µmol/L		≥ 1.5 × ULN
B-urea nitrogen (BUN)	BUN	mmol/L		≥ 11
S-uric acid (urate)	URATE	µmol/L		≥ 510 (women) ≥ 630 (men)
Electrolytes				
S-sodium (natrium)	SODIUM	mmol/L	≤ 125	≥ 155
S-potassium (kalium)	K	mmol/L	≤ 3.0	≥ 6.0

Laboratory Test	CDISC Term	Unit	PCS Low	PCS High
S-calcium	CA	mmol/L	≤ 1.8	≥ 3.0
S-chloride	CL	mmol/L	≤ 90	≥ 117
S-magnesium	MG	mmol/L	≤ 0.6	≥ 1.3
S-phosphate (phosphorus, (inorganic)	PHOS	mmol/L	≤ 0.65	≥ 1.95
S-bicarbonate	BICARB	mmol/L	≤ 12	≥ 38
Endocrine / Metabolic				
B-glucose, non-fasting/unknown	GLUC	mmol/L	≤ 3.4	≥ 9.4
B-glucose, fasting	GLUC	mmol/L	≤ 3.0	≥ 6.0
S-glucose, non-fasting/unknown	GLUC	mmol/L	≤ 3.9	≥ 11.1
S-glucose, fasting	GLUC	mmol/L	≤ 3.5	≥ 7.0
B-glycosylated haemoglobin, fasting	HBA1C	Hb fract.		≥ 6.5
S-prolactin	PROLCTN	mIU/L		≥ 1350
S-thyrotropin/TSH	TSH	mIU/L	≤ 0.3	≥ 5.5
S-protein (total)	PROT	g/L	≤ 45	≥ 95
S-albumin	ALB	g/L	≤ 27	
Lipids				
S-cholesterol total, non-fasting/unknown	CHOL	mmol/L		≥ 7.8
S-cholesterol total, fasting	CHOL	mmol/L		≥ 6.2
S-triglycerides, non-fasting/unknown	TRIG	mmol/L		≥ 5.65
S-triglycerides, fasting	TRIG	mmol/L		≥ 4.2
S-LDL cholesterol, non-fasting/unknown	LDL	mmol/L		≥ 5.3

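### The PCS summary for laboratory tests and absolute ECG limits ignores baseline PCS status, so in this single-arm trial the percentage cannot separate persisting from new abnormalities

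*SAP*

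**What the plan says.** SAP Panel 2 lists, among the primary endpoints, "potentially clinically significant (PCS) clinical safety laboratory test values, vital signs, weight changes, and ECG parameter values". Protocol section 16.9.2 plans only a plain tabulation: "The number of patients exceeding the PCS values will be tabulated". SAP section 14.2 sets the counting rule: "The number and percentage of participants with at least one PCS value at any post-baseline assessment time point will be summarized by variable". It adds: "All available assessments will be included in the evaluation of PCS values". Denominators "will be based on the number of participants with non-missing values at a given visit or during the assessment period". Sections 14.3.1, 14.4 and 14.5 add no baseline-by-post-baseline shift table and no restriction to new cases.

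The PCS limits are in SAP Appendix III. Table 1 (laboratory) uses fixed limits or multiples of the reference limits throughout; the row "S-cholesterol total, fasting", for instance, is met at 6.2 mmol/L or above whatever the baseline value. In Table 3, PR (260 ms or more), QRS (150 ms or more) and QT (500 ms or more) are fixed limits. QTcB and QTcF are met below 300 ms, above 500 ms, or by an increase of more than 60 ms. ECG heart rate needs both a limit and a change from baseline. Weight and most vital-sign criteria in Table 2 also need a change.

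**The concern.** In a controlled trial the comparator would show how many participants exceed a limit regardless of treatment. Here the only within-trial reference is each participant's own pre-dose status, and the summary does not use it. For a fixed limit, the reported percentage combines participants whose abnormality persisted or recurred with participants who crossed the limit for the first time.

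The SAP does use pre-dose status for other primary safety endpoints. Adverse events must start, worsen or become serious from the first dose onwards (14.1.3). C-SSRS results are shown separately for lifetime, past month, baseline and post-baseline (14.6.1). Pre-existing antibodies are summarised (chapter 15). The PCS counts on fixed limits have no counterpart. At stake is what a primary-endpoint table can support: a high percentage could be mostly background, and a real rise in new cases could be hard to see against that background.

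**Working it through.** **Plan's own figures.** The documents state no expected PCS rate, so there is none to reproduce. The only design figure used is the number treated, 100 / (1 − 0.20) = 125 (SAP chapter 20), and only to turn percentages into counts. I assume that all 125 have a post-baseline value.

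**Assumed inputs** (the documents give none), for one variable with a fixed limit:
- b = proportion PCS at baseline
- s = probability that such a participant has a PCS value again after baseline
- r = proportion of the remaining participants who become PCS

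**Formula.** Under the section 14.2 rule, the expected percentage is b·s + (1 − b)·r. The excess over the new-onset rate is b·s + (1 − b)·r − r = b·(s − r), which is positive whenever b > 0 and s > r. Among participants not PCS at baseline, the rate is r.

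**Results with s = 0.8 and r = 2%:**

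| b | b·s | (1 − b)·r | Reported | Pre-existing share of cases |
|---|---|---|---|---|
| 0% | 0% | 2.00% | 2.0% | 0% |
| 2% | 1.6% | 1.96% | 3.6% | 45% |
| 5% | 4.0% | 1.90% | 5.9% | 68% |
| 10% | 8.0% | 1.80% | 9.8% | 82% |
| 20% | 16.0% | 1.60% | 17.6% | 91% |

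At b = 10% the table would show about 12.3 of 125 participants. Of these, 125 × 0.10 × 0.8 = 10 were PCS at baseline and about 2.3 are new, out of 112.5 not PCS at baseline (2.0%).

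**Range.** At b = 10% and r = 2%, s = 0.5 gives 6.8% and s = 1.0 gives 11.8%. At b = 10%, s = 0.8 and r = 5%, the table shows 12.5% against 5.0% new onset.

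**Masking.** With b = 10% and s = 0.8, doubling r from 2% to 4% moves the reported figure from 9.8% to 0.08 + 0.90 × 0.04 = 11.6%. A doubling of new cases appears as a rise of about one fifth (11.6 / 9.8 = 1.18).

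**Where b can exceed zero.** Exclusion 22 (Protocol 5.3) sets numeric limits at screening only for creatinine, bilirubin, ALT and AST, plus a general clause on values posing a potential safety risk. Exclusion 23 removes ECGs that the investigator judges clinically significant. Lipids, glucose, HbA1c, GGT, CK and haematology have no numeric entry limit.

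**The case against.** The strongest reply is that the planned count misses no new case, is labelled post-baseline rather than treatment-emergent, and is one of several descriptive outputs. Absolute values and changes are summarised by visit with quartiles and extremes. Everyone with a post-baseline PCS value has all values of that variable listed with flags. QTcF has its own categorical tables, including increases above 30 and 60 ms. Abnormalities that the investigator finds clinically significant are recorded as adverse events (Protocol 9.6.1) and analysed as treatment-emergent. Exclusions 16 (cardiovascular disease), 17 (other clinically relevant disorders), 22 and 23 keep some abnormal participants out.

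Most of this stands, and it limits the point. It does not supply the missing count. By-visit statistics do not say how many counted participants are new: if 10% exceed a limit at baseline, the upper quartile lies inside the limit and only the maximum shows an excess. Listings allow the split only participant by participant. A PCS value that the investigator does not consider clinically significant need not become an adverse event.

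Three stronger readings should be resisted:
- A reader might infer that any pre-dose PCS value is counted. It is not; a PCS value must occur again after baseline.
- A reader might infer that the whole PCS endpoint is affected. ECG heart rate, the QTc increase criterion, weight and most vital signs already require a change.
- A reader might infer from Protocol 3.2, which says "lifestyle related diseases like metabolic disease, gastric ulcer, menstrual diseases in women and visual disorders are being more frequently reported in cCH", that baseline PCS values are common. That sentence compares chronic with episodic cluster headache and gives no prevalence, so it supports plausibility but no particular value of b.

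**Conclusion.** The point holds for the Table 1 laboratory criteria and for the PR, QRS, QT and absolute QTcB/QTcF limits. For these, the section 14.2 percentage mixes persisting with new abnormalities, and no planned summary separates them. The direction is certain whenever some participants are PCS at baseline and they are more likely than the rest to be PCS afterwards. The size is not known: 3.6% or 9.8% against a new-onset rate of 2% are illustrations with assumed b, s and r. The practical weight falls on lipids, glucose, HbA1c, GGT, CK and haematology. It is smaller for creatinine, bilirubin, ALT, AST and ECG, where Exclusions 22 and 23 apply.

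This is a gap in the presentation of a primary endpoint, worth closing before the tables are produced. It does not make the planned count wrong as labelled, and the documents do not claim that the counted values arose on treatment.

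**What to change.** In SAP 14.2, keep the planned count. For criteria without a change-from-baseline condition (all of Table 1; PR, QRS, QT and the absolute QTcB/QTcF limits in Table 3), add:

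1. The number and percentage with a post-baseline PCS value among participants not PCS in that direction at Baseline, as defined in SAP 3.1, who have at least one post-baseline value.
2. A separate row for participants PCS at Baseline, showing how many were PCS again and how many had a post-baseline value more extreme than Baseline in that direction. Without the second figure, marked worsening in someone already over the limit would go unseen.

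State that each value is classified by the limit for its own fasting status, since Table 1 limits for lipids and glucose differ by fasting and Protocol Panel 5 asks for fasting only when possible.

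The cost is SAP wording, one or two extra rows per table, and a slightly smaller denominator for the emergent count. All data are already collected. Because SAP 3.1 takes the later pre-dose value, a participant PCS at Screening but not at Baseline can still be classed as emergent; a footnote should say so. Without a control arm, the emergent percentage still cannot be attributed to eptinezumab.
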